1.1 Study Objectives

The goal of the project is to enhance capacity to use electronic health record (EHR) data and patient-reported outcomes (PROs) to conduct opioid-related research in Emergency Departments (EDs). Hugo is a cloud-based platform that engages patients as data partners and automates a process that enables patients to easily and securely collect and share health information—including medical records, pharmacy data and survey data such as PROs—directly from a patient’s mobile devices or computer. This pilot study will explore the feasibility and usability of Hugo in integrating electronic health records and pharmacy records with patient reported outcomes in ED patients with nonmedical opioid use, opioid use disorder and/or or opioid overdose.

Primary Objective: The primary objective is feasibility testing to determine whether ED patients with opioid use disorder (OUD), non-medical opioid use or opioid overdose will be willing to share electronic health data with researchers and complete PROs delivered by a mobile-based technology platform.

Secondary Objective: The secondary objective is to collect and measure PROs to better understand factors associated with OUD referrals and treatment.

Exploratory Objective: The exploratory objective is to pilot test the integration of PROs into our ED clinical workflow that will be triggered based on PROs collected by surveys.

1.2 Study Design and Outcomes

This is a single-center observational study that will be conducted in the Yale-New Haven Hospital (YNHH) York Street Campus (YSC) and Saint Raphael Campus (SRC) Emergency Departments (ED)s using a convenience sample. It is an exploratory pilot project designed to inform and enhance the use of EHR data and PROs to conduct opioid-related research in the ED.

1.3 Sample Size and Study Population

This study will include approximately 200 ED adult patients with OUD or non-medical opioid use, or those who are being treated for opioid overdose. Given the exploratory nature of this pilot study, the sample size was chosen based on feasibility rather than a formal power analysis.

1.4 Assessment and Duration

The duration of active participation in this study is one month and includes a baseline, one week and 30-day electronic survey. However, researchers will have access to participants’ EHR and pharmacy data through Hugo for up to one year after enrollment. The study is estimated to last one year, which includes enrollment and follow-up, data analysis, and manuscript development as outlined below.

3/1/2019 - 4/1/19	Yale IRB Submission/Approval
4/2/19 - 4/12/2019	OHRP Approval
4/15/2019 - 4/30/19	Pilot Enrollment (10 subjects)
5/1/2019 - 10/31/19	Full-time Enrollment (190 subjects)
10/31/19 - 12/31/19	Follow-up Completion (Surveys and EHR extraction)
1/1/20 - 2/28/20	Data Cleaning, Lock, Analysis
3/1/19 - 5/29/20	Manuscript Development

1.5 Safety Reporting

As a minimal risk observational, non-medication and non-intervention study, we will only collect information as reported through the EHR and the PRO and not actively collect adverse event or serious adverse event information. Should any unexpected adverse events occur, they will be reported to the Yale IRB as outlined in the DSMP.

1.6 Analyses

As a pilot feasibility study, we will conduct analyses to assess key outcomes outlined above such as enrollment and survey response rates, in addition to outcomes measured by PROs such as treatment continuation and prescription fulfillment.

INTRODUCTION

1.7 Background and Significance to the Field

In the context of the current opioid overdose crisis, the emergency department (ED) is a key venue to address morbidity and mortality related to substance use disorders. Between 2005 and 2014, the rate of opioid-related ED visits increased 99.4 percent (Weiss, et. al., 2016). Patients with opioid use disorder (OUD) are at risk for high ED utilization. Patients with OUD in an integrated health system were reportedly 7.63 times more likely to have an ED visit compared with controls and 5 times more likely to use ED services (Bahorik, et. al, 2017). It is imperative to examine protocols and processes in emergency medicine settings to address the misuse of pharmaceutical and illicit drugs and improve linkage to treatment.

The field of substance use research should pursue approaches to take advantage of data analytics advances in medicine. The National Drug Abuse Treatment Clinical Trials Network (CTN) is supporting studies designed to build capacity to leverage electronic health records (EHR) for research and to promote “learning healthcare systems” so that practice can inform research and data can inform practice and improve quality of care. There are challenges in using EHR data for research and to optimize patient outcomes in the field. The inclusion of opioid relevant common data elements (CDE)s in clinical data registries and EHRs would improve the quality of research in the field. Researchers in the field need to be able to use outcome data points that are already in the EHR, that is, collected as a part of clinical practice. EHR vendors have been slow to incorporate CDEs related to OUDs and clinical data on OUDs is not being collected in a uniform format. Inconsistencies abound in terminology and the types of information recorded about patients.

Patient-reported outcomes are receiving increasing attention. For example, the HealthMeasures (<http://www.healthmeasures.net/>) suite of assessments, developed with substantial support from the National Institutes of Health (NIH), is an important resource for assessment and tracking of patient outcomes. The NIH HealthMeasures program consists of four precise, flexible, and comprehensive measurement systems that assess physical, mental, and social health, symptoms, well-being and life satisfaction; along with sensory, motor, and cognitive function.

The NIH PROMIS and NIH Toolkit are included in this group of resources for collecting patient-generated health data. These measures are becoming available in Epic, Cerner, and MyChart EHR systems for point of care use (Jensen, et. al., 2016; PCORI User’s Guide, 2017). Research is demonstrating how PROMIS computer adaptive tests (CATs) can improve patient care such as how preoperative PRO scores predict the likelihood of obtaining a meaningful benefit from surgery (Baumhauer, 2017).

This project will explore the feasibility of collecting patient-reported outcomes electronically. Hugo (<http://hugophr.com/>) will be used for PRO collection, tracking and data integration. Hugo is a cloud-based platform that engages patients as data partners and automates a process that enables them to easily and securely collect and share health information— including medical records, and survey data such as PROs—directly from a patient’s mobile devices. Unlike traditional patient survey tools, Hugo enables linkage with the Epic EHR to support observational studies linking PRO measures to clinical data. In addition to being publicly available for personal use as a way to access personal medical records, Hugo has been used in multiple studies at Yale University and other academic institutions to deliver electronic surveys and collect data from electronic medical records and pharmacies related to a variety of health-related issues, such as heart disease and diabetes.

Hugo Overview, Testing and Acceptability

There are groups that are emerging with the intent to integrate data on behalf of patients and enable those data to be synchronized with the research data but they have yet to establish and validate their data. The Hugo team has several distinguishing features that make their platform preferable over other available systems, such as REDCap DDP, including 1) their track record with industry, academic partners and the FDA and demonstrated ability to integrate data from disparate sources using current APIs and with the capacity to leverage next generation standards; 2) their focus on participant partnership, providing people with agency over their health data; 3) their commitment not to move data without people’s permission – the approach ensures that people retain control over how their data are used; 4) their development of Hugo Harmony, an AI approach to improving data quality; 5) their commitment to security and privacy and use of state-of-the-art cloud-based approaches; 6) their design which does not require agreements with health systems or other data holder, but rather leverages the rights of individuals to access their data – and builds on rights from HIPAA, HITECH Act and the 21st Century Cures Act; 7) their ability to provide almost real-time data streams, which provide rapid information about outcomes; and 8) their experience in obtaining high response rates using digital devices, with data being encrypted in motion and at rest; 9) their highly regarded user interface; and 10) their method of making it easy to create new surveys without the need for knowledge of a programming language. Of note, REDCap DDP barriers include burdensome setup and ongoing maintenance requiring time and resource investment from the research team and potentially from busy IT resources at research sites.

The Hugo platform has been used across a range of studies to engage populations of varying backgrounds and currently has more than 1,000 users. The age range in prior studies generally ranged from 20 to 80 years, suggesting an acceptability across ages. Hugo is currently in use by several industry, foundation and FDA sponsored studies. With respect to reach, in a study funded by the Aetna Foundation, in partnership with Project Access New Haven, Hugo was used to understand its acceptability to lower health literacy populations. The results showed that this group were avid adopters of the technology, reported being empowered by being given agency over their data, and participated with high response rates (>80%), which were similar for the Spanish version of the platform. Overall, projects using Hugo have typically had ePRO response rates as high as 70% on initial delivery of survey questions. When automated reminders were sent to study participants who did not initially respond, response rates increased further to 80% and above. In some studies response rates through mobile delivery have reached 90% and higher.

Several studies involving Hugo validated the EHR data from Hugo with EHR data collected through traditional methods. As an example, one industry-sponsored project found a 100% match between patient demographic and medical history and event data captured through Hugo and data collected from manual abstraction from the EHR. Importantly, Hugo enabled the capture of events almost immediately after they occurred.

*Note that the statistics referenced above are not currently published in peer-reviewed journals but are private data provided by Hugo, based on their experience and internal evaluation of their platform.

Site Selection:

Yale New Haven Health (YNHH) provides health care to children and adults living in the southern portion of Connecticut, from the New York border to Westerly, Rhode Island. The Yale New Haven Health Emergency Departments at the York Street and Saint Raphael locations provide service to the Greater Bridgeport, New Haven and New London catchment areas. In 2016, 240,000 (19%) individuals within this catchment area received emergency or primary care from YNHHS. Of these, 8,503 unique patients had a diagnosis of alcohol use (AUD) and 1,020 of opioid use disorder (OUD). Forty-three percent of the more than 9,000 SUD patients identified in our EDs were seen two or more times in that year.

Study Rationale:

Given limitations of EHR data related to OUD, this study is designed to inform enhancements to EHR and PROs. We hypothesize that ED patients with OUD, non-medical opioid use, or those who are being treated for opioid overdose will be willing to provide PROs after ED discharge using the electronic platform Hugo, and these PROs can be used to enhance patient care.

OBJECTIVES

1.8 Primary Objective

The primary objective is feasibility testing to determine the proportion of ED patients with OUD, non-medical opioid use or overdose who are willing to share electronic health data with researchers and complete PROs delivered by a mobile-based technology platform. We hypothesize that patients will be willing to enroll and provide PROs both during and after discharge. The primary objective will be measured by the proportion of people who qualify for study criteria and enroll in the study by signing up for Hugo and sharing their EHR with researchers for this study, as well as response rates to electronic surveys and lost-to-follow-up (LTFU) rates among those who enroll. If successful, electronic PROs could offer an opportunity to improve follow-up and treatment among patients with OUD after discharge from the ED.

1.9 Secondary Objectives

The secondary objective is to collect and measure PROs to better understand factors associated with OUD referrals and treatment. Sample outcomes to be measured by surveys include patient experience and ED care, proportion of participants receiving medications for OUD in the ED and referral to treatment by self-report, attendance at follow-up treatment appointment, and post-ED prescription medication pickup.

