1.11 Overview of Study Design

Overview:

The Hugo platform will deliver a link to survey in Hugo via email or text message to approximately 200 patients that have been registered as Hugo users by ED and/or research staff and enrolled in the study. Surveys will be delivered to participants at three separate timepoints (baseline, within one week and 30 days following enrollment).

Progression of study design:

As part of the study design, survey timing and content will be changed or updated periodically based on 1-2 month cycles of iterative testing (i.e., up to a total of 4 unique PROs will be delivered throughout the study period) to allow the research team to assess success of specific measures for a particular population and make survey response and patient contact data available to the research team to facilitate patient engagement and action. All questions will be derived from the list of potential PROs included as attachments (Baseline Survey, Survey 2, Survey 3) to this submission and timing of survey distribution may change based on feedback (i.e., 2-day survey may be delivered at 3 or 4 days, if more feasible or appropriate based on PROs delivered). Changes will not compromise the ability to measure outcomes previously described but will be implemented as necessary based on knowledge and experience throughout the study.

A sample timeline for iterative testing includes:

Iteration 1: May 1 – June 30, 2019
Iteration 2: July 1 – Aug 31, 2019
Iteration 3: Sept 1 – Oct 31, 2019
Iteration 4: Nov 1, 2019 – Dec 31, 2019

Sample iterations of PROs include:

Iteration 1:

Baseline survey: Delivered upon enrollment and includes contact information, overdose question, DSM-V criteria for OUD

Survey 2: Delivered 2 days post-enrollment (or 2 days post hospital discharge if the participant was admitted from the ED at enrollment) and includes review of ED care, linkage with treatment and prescriptions post-discharge, and changes in behavior (i.e., TEA assessment)

Survey 3: Delivered 30 days post-enrollment (or 30 days post hospital discharge if the participant was admitted from the ED at enrollment) and includes linkage with treatment and prescriptions, overdose history, and changes in behavior (i.e., TEA assessment)

Iteration 2:

Baseline survey: Same as above

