1.14 Secondary Outcome Measures

PRO measures, such as patient experience, TEA assessment, and the proportion of participants receiving OUD medication and referral in the ED, enrolling in treatment and refilling prescriptions following their visit.

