5. EHR Data Extraction: In addition to survey data, the following fields will be automatically extracted from participants EHRs: Name, Age, Gender, Date of birth, Medical record number, Vital signs, Provider encounters, Family history, Laboratory findings, Procedures, Problem list, ICD diagnoses, Medicines administered and prescribed. These fields will be used for secondary and/or future exploratory analyses as they relate to PROs and can be extracted as far back as each participant's available EHR.
6. Pharmacy Data Extraction: Prescription refill data will be automatically extracted from participating pharmacies that currently share data with Hugo, such as CVS and Walgreens, and are linked to each participant's Hugo account. Available prescription data will be used for secondary and/or future exploratory analyses as it relates to PROs.
7. Case Report Form – Enrollment: Used to document whether participants required assistance setting up a MyChart or pharmacy account to be linked with Hugo.

8. Case Report Form – Follow-up Call: Used to document information collected during follow-up calls, when applicable.

TRAINING REQUIREMENTS

All study personnel such as LI, co-lead investigators, study RA, project managers and data analysts will be listed on the Yale IRB submission. Per Yale IRB policies, all staff must have completed HIPAA training, Human Subjects Protection Training, Good Clinical Practice Training and a conflict of interest form (investigators only) for the submission to be approved. In addition to these trainings, the LI will provide protocol specific training and ensure that all staff understand the study protocol and follow all guidelines outlined in this document.

STATISTICAL DESIGN AND ANALYSES

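### Receipt of OUD medication in the ED is measured by self-report from Survey 2 responders, although the EHR feed extracts medicines for enrollees who link their YNHH record

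*Protocol*

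**What the plan says.** Section 1.9 opens its list with "Sample outcomes to be measured by surveys include patient experience and ED care" and goes on to the "proportion of participants receiving medications for OUD in the ED and referral to treatment by self-report". Section 1.14 repeats the item among the PRO measures as "the proportion of participants receiving OUD medication and referral in the ED". Both take participants as the denominator.

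Under the sample iteration in section 1.11, Survey 2 goes out 2 days after enrollment, or after hospital discharge for those admitted, and "includes review of ED care, linkage with treatment and prescriptions post-discharge". The baseline survey in that iteration holds contact information, an overdose question and the DSM-V criteria. It has nothing on ED treatment.

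Study Assessments item 5 lists the fields pulled automatically from the EHR, including "Problem list, ICD diagnoses, Medicines administered and prescribed". On their use it says: "These fields will be used for secondary and/or future exploratory analyses as they relate to PROs". The data management text in section 1.11 adds, in general terms, that survey, EHR and pharmacy data will all serve to assess the outcomes.

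**The concern.** Whether a patient received OUD medication in the ED is a fact of the index visit, normally entered in the hospital record. The protocol takes it from a questionnaire sent after the patient has left. Anyone who does not answer Survey 2 drops out of the numerator and the denominator, and the result describes responders under a label that says participants.

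It is plausible, though not shown, that patients who were started on medication are more engaged and more likely to answer. The proportion would then be too high for the enrolled group. A reader could take it as the treatment rate among enrolled ED patients and plan later studies on it, although a source that does not depend on survey response was in the same database.

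**Working it through.** **Is there a figure to reproduce?** No. Section 1.3 sets about 200 participants on feasibility grounds, with no precision target. The enrollment arithmetic in section 1.4 agrees: 10 + 190 = 200.

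**Which source is named?** The closing words of the phrase in 1.9 could be read as applying to referral only. The lead-in of the list settles it, because every item there is measured by surveys, and 1.14 files the item under PRO measures.

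**Inputs.** N = 200 (section 1.3). Response r = 70% at first delivery, 80% after reminders and 90% in some studies (Hugo overview, section 1.7; unpublished platform data from other projects). The protocol gives no receipt rate and no responder/non-responder difference. I assume a receipt rate of 30% and gaps d of 10, 20 and 30 points.

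**Bias.** With receipt p_R in responders and p_N in non-responders, the proportion among all enrolled is r·p_R + (1 − r)·p_N. Hence

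bias = p_R − [r·p_R + (1 − r)·p_N] = (1 − r)(p_R − p_N) = (1 − r)·d.

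**Worst-case range.** For an observed proportion p, the proportion among all enrolled lies between r·p (no non-responder treated) and r·p + (1 − r) (all treated).

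**Sampling error.** 95% half-width = 1.96·√(p(1 − p)/n), with n = 200r.

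| Response | n | Bias for d = 10 / 20 / 30 points | Range for observed 30% | Half-width at 30% |
|---|---|---|---|---|
| 70% | 140 | 3 / 6 / 9 points | 21–51% | 7.6 points |
| 80% | 160 | 2 / 4 / 6 points | 24–44% | 7.1 points |
| 90% | 180 | 1 / 2 / 3 points | 27–37% | 6.7 points |
| all 200 observed | 200 | 0 | 30% | 6.4 points |

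For example, at 70% response and d = 20: (1 − 0.70) × 20 = 6 points; range 0.70 × 0.30 = 0.21 to 0.21 + 0.30 = 0.51.

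**Effect on interval coverage.** Take a true 30% and a 20-point gap. At 70% response the expected responder proportion is 36%, its standard error √(0.36 × 0.64/140) = 0.0406, and bias/SE = 0.06/0.0406 = 1.48. Coverage of the nominal 95% interval is Φ(1.96 − 1.48) − Φ(−1.96 − 1.48), about 68%. The same steps give about 81% at 80% response and 91% at 90%.

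**How complete is the EHR source?**
- For: section 1.8 makes sharing the EHR part of enrolling. Section 1.22 has the RA help set up a YNHH MyChart account where needed. Section 1.24 has all participants agree to share EHR and pharmacy data.
- Against: section 1.21 speaks of releasing EHR data, pharmacy data or both, and under 1.22 participants choose which systems to link.
- Window: item 5 allows extraction as far back as the record goes. Appendix B, section 2.0 (Study Specific Risks), limits access to data from enrollment onward. Patients may be approached after the clinician's evaluation (1.20.1) and enrolled on the inpatient floor (1.19), so medication given earlier in the index visit could fall outside the second window.

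**How much under-capture would cancel the gain?** If the feed misses a share m of true receipts, the EHR proportion at a true 30% is low by 30·m points. That equals the 6-point survey bias (70% response, 20-point gap) at m = 6/30 = 20%, and the 4-point bias (80% response) at m = 4/30 = 13%.

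**The case against.** The strongest reply is that measuring PROs is the secondary objective itself, and the Study Rationale justifies it by the limits of EHR data on OUD. That stands: collecting self-report is not an error and should continue. The rationale does not say that medication records are the weak part, however, and reporting the EHR figure beside the self-report serves the aim of improving both sources.

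A second reply is that section 1.11 says all three data sources will assess the outcomes, and item 5 assigns EHR fields to secondary analyses. A reader might infer from 1.9 that the EHR is barred for this outcome. The protocol does not go that far. Nor does the general sentence in 1.11 displace the specific survey measurement in 1.9 or set a denominator for an EHR-based figure.

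A third reply is that follow-up effort is substantial: up to three reminders, an RA call, a secondary contact and payment per survey. This may well bring response to 80% or more, which shrinks the bias but does not remove it.

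Two further inferences should be resisted. One is that the EHR already holds this item for every enrolled participant; the wording in 1.21 and the conflict over the extraction window leave that open. The other is that the criticism covers referral and appointment attendance. Neither is a named extraction field, so self-report remains the planned source for both.

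**Conclusion.** The point holds for one outcome, receipt of OUD medication in the ED. As written, it is a responder-only proportion with participants as its stated denominator, and the protocol already extracts a source free of survey non-response for enrollees who link their YNHH record.

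Bias is possible, not certain. It needs response to be related to receipt. Under the assumed gaps of 10 to 30 points it is 3 to 9 points at 70% response and 2 to 6 points at 80%. At the larger gaps this is about the size of the sampling error. With no gap it is zero. The response rates come from other projects on the platform, and the gaps and the 30% receipt rate are assumptions.

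The advantage of the EHR depends on linkage and on the extraction window covering the index visit. This is one sample secondary outcome of a descriptive pilot, and the feasibility conclusions on enrollment, response and follow-up do not depend on it. I class it as a cheap improvement.

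**What to change.** 1. Before anything else, reconcile Study Assessments item 5 with Appendix B, section 2.0, on how far back EHR data are accessible, so that medication given in the index ED visit before enrollment is captured. Align the consent wording if it is affected.
2. In 1.9, 1.14 and Statistical Design and Analyses, report ED-administered or ED-prescribed OUD medication from the EHR. Use all enrollees with a linked YNHH record as the denominator, and state how many are unlinked.
3. Report the self-reported proportion beside it, with survey–EHR agreement among responders.
4. Compare Survey 2 responders with non-responders on EHR receipt. This replaces the assumed gap above with an observed one.
5. Leave referral and appointment attendance as self-reported outcomes, labelled as responder estimates.

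The cost is protocol wording and a modest extra analysis of fields already extracted, with no new data collection. The downside is dependence on linkage and on the extraction window: if the narrower window is the true one, the EHR figure could be too low and must be labelled accordingly.
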